## 8.2 Analysis of Study Population and Subject Characteristics

Enrollment, major protocol violations, and discontinuations from the study will be summarized. Demographic and baseline characteristics, such as age, sex, race, weight, disease characteristics and markers of organ function at Screening will be summarized using means, standard deviations, medians, ranges for continuous variables, and proportions for categorical variables.

## 8.3 Analysis of Efficacy Endpoints

### 8.3.1 Primary Efficacy Analysis

This stratified randomized double-blind phase 2b study has as its primary efficacy endpoint confirmed renal response at the confirmatory EOS visit to evaluate 12 months of study treatment. The primary efficacy analysis will test the following hypotheses:

- $H_0$ : The confirmed renal response rate after 12 months of treatment is equal between placebo and NEOD001.
- $H_1$ : The confirmed renal response rate after 12 months of treatment is different between placebo and NEOD001.

The primary efficacy analysis of the confirmed renal response rates after 12 months of treatment with NEOD001 or placebo will be performed with the Mantel-Haenszel (MH) test at the alpha=0.05 (two-sided) level of significance. The analysis will be stratified by the randomization stratification variables. The number and percentage, with associated 95% exact confidence intervals (CI) of subjects in each category of response will be presented by treatment group. The proportional treatment difference with associated exact 95% CI will be presented.

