### **3.4 Randomization and Blinding**

#### **3.4.1 Randomization**

A subject number will be assigned via a web-based registration for each subject who has signed an informed consent form (ICF). If a subject has completed all screening requirements and meets all of the eligibility

criteria, a Subject Registration Form will be submitted to the medical monitor for eligibility review and approval. If approved, randomization will be implemented via the Internet connection. At least 100 subjects will be randomized in a 1:1 ratio into one of two arms, NEOD001 24 mg/kg (50 subjects) or placebo (50 subjects). The randomization will be stratified by two factors:

- Hematologic response: Complete response/very good partial response (CR/VGPR) vs partial response (PR) to therapy (Appendix 1)
- Renal stage: Stage 1 and 2 vs stage 3 (Appendix 1, Palladini 2014)

Upon successful randomization, the Unblinded Pharmacist or their designee (henceforth collectively referred to as the Unblinded Pharmacist) will be provided with the treatment assignment. Numbers assigned to subjects who do not receive study drug will not be re-used.

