## **4.0 SELECTION, DISCONTINUATION, AND WITHDRAWAL OF SUBJECTS**

### **4.1 Inclusion Criteria**

Subjects must meet **all** of the following criteria:

1. 18 years of age or older
2. Biopsy-proven diagnosis of AL amyloidosis by immunohistochemistry or mass spectroscopy of a tissue biopsy excluding bone marrow
3. Screening renal biopsy for RAIN confirming AL amyloidosis as exclusive or dominant cause of renal damage
4. Persistent renal involvement with proteinuria (predominantly albumin) > 500mg/day in a 24-hour urine collection
5. CKD 1, 2 or 3
6. ≥1 prior systemic hematologic therapy for free light chain (FLC) producing hematologic malignancy underlying the initial diagnosis of AL amyloidosis with a FLC response to treatment (PR, VGPR, CR) that is deemed stable and not requiring further treatment
7. ECOG Performance Status ≤ 2
8. Clinical laboratory values:
  - Absolute neutrophil count > 1000/µL
  - Platelet count > 75,000/µL
  - Total bilirubin ≤ 1.5X ULN
  - Alkaline phosphatase ≤ 5X ULN
  - ALT or AST ≤ 3X ULN
  - NT-proBNP < 1800 pg/mL
9. Voluntary written consent must be given before performance of any study-related procedure not part of standard medical care with the understanding that consent may be withdrawn by the patient at any time without prejudice to future medical care.

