#### **8.5. Determination of Sample Size**

This stratified randomized double-blind phase 2b study has as its primary efficacy end-point the confirmed renal response rate at 13 months after initiating therapy and is designed to detect an absolute increase in the renal response rate of 30% (from 25% in those receiving placebo to 55% in those receiving NEOD001). For the primary efficacy endpoint, the assumed true rates for NEOD001 vs placebo are 55% and 25%, respectively. Based on a chi-squared statistic to evaluate the null hypothesis at the alpha=0.05 level of significance, and assuming an 18% drop-out rate for hematologic progression requiring chemotherapy, a total sample size of 82 subjects (41 in the placebo group, 41 in the NEOD001 group) will enable us to reject the null hypothesis that the response rates for subjects receiving NEOD001 and placebo are equal with probability (power) 0.8. With 50 patients receiving placebo and 50 patients receiving NEOD001, we expect to have at least 41 evaluable patients in each group.

Of note, we are estimating the renal response rate over time in the arm not receiving NEOD001. In the relapsed setting, patients receiving lenalidomide and dexamethasone had an 18% renal response rate at 6 and 12 months; an additional 18% responded by 18 months. In relapsed patients receiving cyclophosphamide, lenalidomide and dexamethasone, 19% had renal responses, while in a phase 1/2 trial in relapsed patients (N=70) treated with bortezomib, 29% had a renal response. In the initial therapy setting, patients with renal involvement who received cyclophosphamide, bortezomib and dexamethasone (CyBorD) had a 25% renal response rate. Post-ASCT with bortezomib-based consolidation, while 50% of renal patients respond by the end of the first year, an additional 20% of renal patients respond in the second year post-ASCT. While we do not know the mix of patients who will be screened and enrolled in this trial, it is reasonable to assume that one third will be post-SCT, one third post initial and one third post second-line therapy. Allowing for a 6 month interval after chemotherapy and a 12 month interval after SCT, the weighted average of the renal response rates in these groups is 22.3%. We have chosen a higher estimate (25%) as the confirmed renal response rate in this study in patients receiving placebo.

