#### Stratification for Renal Staging

Test	Value	Score
Proteinuria	≤5 g/24 hours	0
	>5g/24 hours	1
eGFR	≥50 mL/min/1.73 m 	0
	<50 mL/min/1.73 m 	1
Total Score		0 = Renal Stage 1 1 = Renal Stage 2 2 = Renal Stage 3

eGFR = estimated glomerular filtration rate.

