#### Appendix 4 Modified Organ Response and Progression Criteria

Organ	Response	Progression
Heart	NT-proBNP response (>30% and >300 ng/L decrease in subjects with baseline NT-proBNP 2650 ng/L) or NYHA class response (2 class decrease in subjects with baseline NYHA class 3 or 4)	NT-proBNP progression (>30% and >300 ng/L increase)
Renal	>30% decrease in proteinuria or drop of proteinuria below 0.5 g/24 hours in the absence of renal progression	>25% decrease in eGFR

Abbreviations: eGFR = estimated glomerular filtration rate; NT-proBNP = N-terminal pro B-type natriuretic peptide; NYHA = New York Heart Association.

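### The primary test uses baseline 24-hour proteinuria only through a coarse renal-stage split; pre-specifying it as a covariate is a cheap improvement worth about 0 to 5 points of power

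*Combined protocol and SAP*

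**What the plan says.** Section 8.3.1 states that the comparison of confirmed response rates "will be performed with the Mantel-Haenszel (MH) test at the alpha=0.05 (two-sided) level of significance" and that "The analysis will be stratified by the randomization stratification variables". Section 3.4.1 names two factors: "Hematologic response: Complete response/very good partial response (CR/VGPR) vs partial response (PR) to therapy" and "Renal stage: Stage 1 and 2 vs stage 3".

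The staging table in Appendix 1 gives one point for proteinuria above 5 g/24 hours and one for eGFR below 50, and maps the total as "0 = Renal Stage 1 1 = Renal Stage 2 2 = Renal Stage 3". Stage 3 therefore needs both.

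Entry under section 4.1 requires "Persistent renal involvement with proteinuria (predominantly albumin) > 500mg/day in a 24-hour urine collection", with no upper limit. Appendix 4 defines renal response as a fall of 30% in proteinuria or "drop of proteinuria below 0.5 g/24 hours in the absence of renal progression". Table 1 schedules a 24-hour urine protein collection at screening for every patient. Sections 8.3.1 to 8.6 name no covariate-adjusted analysis of the primary endpoint.

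Section 8.5 sizes the trial on an unadjusted chi-squared test: "the assumed true rates for NEOD001 vs placebo are 55% and 25%, respectively", 41 evaluable per arm, power 0.8, 50 per arm randomized to allow for 18% dropout.

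**The concern.** The strata carry little information on proteinuria. A patient at 0.6 g and one at 12 g, both with eGFR 60, score 0 and 1, so they are stages 1 and 2 and share a stratum. Yet each patient's response is judged against the baseline value, and the fall required depends on it near the entry limit. If baseline proteinuria also predicts response within strata, the planned test leaves explainable variation in the error term.

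The second issue is chance imbalance. Section 8.2 will tabulate markers of organ function at screening, but the plan gives no rule for the case where proteinuria differs between arms. An adjustment chosen after seeing that table would be post hoc.

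At stake are some efficiency and the standing of any adjusted result. The validity of the planned test is not in question.

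**Working it through.** **1. Reproduce the plan's figure.** Inputs from 8.5: 25% and 55%, two-sided alpha 0.05, power 0.80. With mean rate 0.40:

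n = (1.96·√(2·0.40·0.60) + 0.8416·√(0.25·0.75 + 0.55·0.45))² / 0.30² = (1.358 + 0.555)² / 0.09 = 40.7, so 41 per arm; 41/0.82 = 50.

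At 41 per arm, SE0 = √(0.48/41) = 0.1082 and SE1 = √(0.435/41) = 0.1030. Power = Φ((0.30 − 1.96·0.1082)/0.1030) = Φ(0.854) = 80.3%. The stated power does not rely on adjustment.

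**2. How the rule depends on baseline.** At 0.55 g, falling below 0.5 g needs a drop of 1 − 0.5/0.55 = 9%. The two routes meet at 0.5/0.7 = 0.71 g; above that, 30% is needed.

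**3. Approximate gain.** Multiply both standard errors by √(1 − R²), where R² is the share of response variance explained by baseline. R² is an assumption. R² of 0.02, 0.05, 0.10 and 0.15 give 81.1%, 82.4%, 84.4% and 86.4%.

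**4. Simulation against the planned test.** 41 per arm, 6,000 runs per scenario, marginal rates 25% and 55%. Assumed: half of patients above 5 g, 35% with eGFR below 50, 30% PR. The logistic tests are likelihood-ratio tests.

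| Odds ratio per SD of log baseline | R², placebo / active | Stratified MH | Logistic, strata only | Logistic, strata + log baseline | Covariate's own gain (points) | Type I error, MH / adjusted |
|---|---|---|---|---|---|---|
| 1.00 | 0 / 0 | 79.6% | 81.6% | 81.4% | −0.2 | 5.1% / 6.2% |
| 0.74 | 0.016 / 0.021 | 80.1% | 81.8% | 82.1% | 0.3 | 5.1% / 6.0% |
| 0.61 | 0.044 / 0.055 | 79.9% | 81.5% | 83.2% | 1.7 | 5.2% / 6.0% |
| 0.50 | 0.081 / 0.099 | 80.3% | 82.2% | 84.7% | 2.5 | 4.5% / 5.6% |
| 0.37 | 0.147 / 0.172 | 79.8% | 81.5% | 86.2% | 4.7 | 4.7% / 5.3% |

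The own gain is the fifth column minus the fourth. About 2 points of the gap from MH come from changing the test, not from the covariate. The Monte Carlo standard error of one power figure is about √(0.8·0.2/6000) = 0.5 points.

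**5. A change-from-baseline model.** Assumed median 4 g, log SD 0.8, one follow-up value, 5,000 runs. For baseline/follow-up correlations of 0.9, 0.8, 0.7 and 0.5, logistic power moves from strata only to strata plus baseline as follows: 81.1% to 82.0%, 81.2% to 83.3%, 82.1% to 84.6%, and 82.4% to 87.7%. The gains are 0.9, 2.1, 2.5 and 5.3 points.

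**6. Choice of adjusted test.** In a separate simulation (5,000 runs), type I error was 5.1-5.6% for a logistic score test and 5.3-5.9% for the standardised risk difference, against 4.2-5.1% for MH.

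**7. Chance imbalance.** The standard error of the standardised baseline difference is √(2/41) = 0.22 SD. A gap beyond 0.3 SD has probability P(|Z| > 0.3/0.22) = P(|Z| > 1.36), about 17%.

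**The case against.** The strongest reply is that the plan is coherent: it analyses as it randomized, reaches its stated power, and takes no credit for covariates, so nothing promised is lost. Randomization protects type I error whatever the chance imbalance. All of this stands.

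A reader might infer that dependence on baseline is built into the response rule and must be strong. With no true change and an assumed within-person log SD of 0.25, the chance of meeting the proteinuria criterion at both visits is about 24% at an observed 0.55 g, 16% at 0.6 g and 6% at 1 g or more. But this concerns only patients entering near the limit. Under assumed medians of 2-5 g and log SDs of 0.6-1.0, about 1-18% enter below 1 g. Regression to the mean works the other way, since a high observed baseline favours an apparent fall. With true change independent of baseline, the correlation of log baseline with response was only about 0.04 to 0.13, and positive. By the step 3 formula, 0.13² = 0.017 gives 81.0%, a gain of under 1 point. The figure depends on how much true change varies between patients; less variation raises it, and it stays positive. A large gain would need prognostic strength beyond the rule, and the documents supply none.

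A reader might also treat adjustment as free. It is not: the test becomes model-based, its type I error is slightly higher at about 82 patients, and a log-linear term will not follow the threshold near 0.5 g closely.

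**Conclusion.** The point holds as an efficiency and pre-specification improvement. The primary test uses baseline proteinuria only through a 5 g cut combined with eGFR below 50, although the value is collected from everyone. The covariate's own contribution is about 0 points of power if it is unrelated or weakly related to response, and about 5 points at an odds ratio near 0.37 per SD. That range rests on assumed associations, stratum shares and proteinuria distributions, because the documents give none of them.

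Two stronger readings are not supported. One is that the trial is underpowered: it has 80.3% on its own inputs. The other is that power near 90% is being given up: the step 3 formula reaches 90.4% only at a correlation of 0.5 (R² 0.25), which nothing in the documents supports. The argument from chance imbalance is modest but does not depend on the power gain.

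**What to change.** Before unblinding, add to 8.3.1, and to the matching synopsis text, a logistic regression of confirmed response on arm, the two stratification factors and log baseline 24-hour proteinuria. Use the same screening value that serves as the reference for response. Report the standardised (marginal) risk difference with a 95% CI, which keeps the result on the difference scale that 8.3.1 already uses.

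Preferably make this the primary analysis and keep the stratified Mantel-Haenszel test, with its exact intervals, as supporting. At minimum, list it as a named adjusted analysis beside the planned primary test. State in advance which result is decisive. Name a score test or a small-sample correction for the treatment effect, and limit continuous covariates to one or two (baseline eGFR is the natural second).

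The cost is SAP wording, with no new data or visits. The price is reliance on a model, with type I error of roughly 5-6% against about 5% for Mantel-Haenszel at this sample size; the choice of test is meant to contain that.

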### 8.3.2 Secondary Endpoint Analyses

Comparisons of mGFR and eGFR at study entry will be by the Tukey mean-difference (Bland-Altman) method determining whether the measurements are sufficiently close at alpha level of 0.05.

Analyses of time-to-event secondary endpoints comparing the NEOD001 and placebo groups will be performed by Kaplan-Meier (stratified log-rank) at an alpha level of 0.05. These endpoints include time to CKD 4 or 5, time to eGFR  $\leq$  15 or dialysis, time to doubling of serum creatinine, and time to  $\geq$  40% reduction in eGFR.

The comparisons of renal response and progression in patients with maintained hematologic responses at 26 months who received NEOD001 or placebo will be analyzed using a standard t-test and also using a Cochran Mantel-Haenszel (CMH) test stratified by the pre-randomization stratification factors. The number and percentage, with associated 95% exact confidence intervals (CI), of subjects in each category of response will be presented by treatment group. The proportional treatment difference with associated exact 95% CI will be presented.

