Statistical Considerations and Methods	
Primary Efficacy Analysis:
 
This stratified randomized double-blind phase 2b study has as its primary end-point the confirmed renal response rate after 12 months of treatment with NEOD001 or placebo and is designed to detect an absolute increase in the renal response rate of 30% (from 25% in those receiving placebo to 55% in those receiving NEOD001).
 
The primary efficacy analysis of the confirmed renal response rates after 12 months of treatment with NEOD001 or placebo will be performed with the Mantel-Haenszel (MH) test at the alpha=0.05 (two-sided) level of significance. The analysis will be stratified by the randomization stratification variables.
 
Secondary Endpoint Analyses:
 
Comparisons of mGFR and eGFR at study entry will be by the Tukey mean-difference (Bland-Altman) method determining whether the measurements are sufficiently close with alpha of 0.05.
 
Analyses of other secondary endpoints comparing patients receiving NEOD001 or placebo will depend on the endpoint. Time-to-event endpoints including time to CKD 4 or 5, to eGFR <math><</math> 15 or dialysis, to doubling of creatinine, and to <math>></math> 40% reduction in eGFR, will be analyzed by Kaplan-Meier (stratified log-rank) with alpha of 0.05.
 
The comparisons of renal response and progression in patients who have had maintained hematologic responses at 26 months will be by MH test stratified by the pre-randomization stratification factors to

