**Figure 1****NEOD001-RAIN Study Design****Stratification:**

- Response to most recent treatment regimen: CR+VGPR vs PR
- Renal stages 1 or 2 vs Renal stage 3

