### Exclusion:

Subjects must **not meet any** of the following criteria:

1. Female patients who are lactating, breastfeeding, or pregnant. Men and women of childbearing potential need to use birth control while participating in the study.
2. Patients who did NOT complete the entire active study period of RAIN
3. Patients who are CKD 4 or 5 or on dialysis (eGFR  $< 30$ )

4. Medically documented cardiac syncope, uncompensated congestive heart failure, myocardial infarction within the previous 6 months, unstable angina pectoris, clinically significant repetitive atrial or ventricular arrhythmias despite antiarrhythmic treatment, or severe orthostatic hypotension or clinically significant uncompensated autonomic insufficiency.
5. Comorbid systemic illnesses or other severe concurrent disease which, in the judgment of the investigator, would make the patient inappropriate for entry into this study or interfere significantly with the proper assessment of safety and toxicity of the prescribed regimens.
6. Ongoing or active infection, known HIV positive, known to be hepatitis B surface antigen-positive or has known or suspected active hepatitis C infection.
7. Psychiatric illness/social situations that would limit compliance with study requirements

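### For time to CKD 4 or 5, the planned stratified log-rank uses baseline eGFR only coarsely; a pre-specified adjustment would recover some power

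*Combined protocol and SAP*

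**What the plan says.** Section 8.3.2 states that the time-to-event secondary endpoints "will be performed by Kaplan-Meier (stratified log-rank) at an alpha level of 0.05", and the synopsis agrees: they "will be analyzed by Kaplan-Meier (stratified log-rank) with alpha of 0.05". Neither place names the strata, states sidedness for this test, or includes a covariate. There are four endpoints: CKD 4 or 5, eGFR 15 or dialysis, doubling of creatinine, and a 40% fall in eGFR.

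Section 3.4.1 stratifies randomisation by hematologic response and by "Renal stage: Stage 1 and 2 vs stage 3"; Figure 1 gives the same split. Appendix 1 scores one point for proteinuria above 5 g/24 h and one for eGFR "<50 mL/min/1.73 m"², then sets "0 = Renal Stage 1 1 = Renal Stage 2 2 = Renal Stage 3". The synopsis admits CKD 1 to 3 with eGFR of at least 30 and sets no upper limit. The extension-study exclusions in Appendix 11 equate CKD 4 or 5 with eGFR below 30. Table 1 collects eGFR on every patient at screening and on month 1 day 1.

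**The concern.** Whether a patient reaches CKD 4 within 13 months depends heavily on how far above eGFR 30 that patient starts. The only renal information in the planned test is a two-level stage, and its lower stratum mixes patients close to the threshold with patients far from it. Baseline eGFR is available for everyone but is not used directly. Some of the treatment contrast is therefore lost in variation that could have been accounted for, on an endpoint for which the plan states no power and few events are likely.

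**Working it through.** **1. The plan's own figure.** The only power statement (Section 8.5) is for the primary endpoint: 55% versus 25%, 41 per arm, power 0.80. With a pooled two-sided test, n = [1.96·√(2·0.40·0.60) + 0.8416·√(0.55·0.45 + 0.25·0.75)]² / 0.30² = (1.358 + 0.555)² / 0.09 = 40.7, so 41 per arm. Then 41 / 0.82 = 50. This reproduces. No event count, hazard ratio or power is given for any time-to-event endpoint.

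**2. What the strata contain** (Appendix 1, with entry eGFR at least 30):

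| | Proteinuria ≤5 g/24 h | Proteinuria >5 g/24 h |
|---|---|---|
| eGFR ≥50 | stage 1 | stage 2 |
| eGFR 30 to <50 | stage 2 | stage 3 |

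Three of the four cells are pooled as stage 1-2, which covers the whole entry range of eGFR.

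**3. Distance to the threshold.** From 32: (32 − 30)/32 = 6%. From 90: (90 − 30)/90 = 67%. With proteinuria of 5 g/24 h or less, both patients are in the stage 1-2 stratum.

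**4. How much baseline eGFR the stage carries.** Assumptions: median eGFR 45-65, median proteinuria 3-6 g/24 h, correlation 0 to −0.3. The stage split explains 9-32% of the variance in baseline eGFR; a plain cut at 50 would explain 46-61%. Between 28% and 74% of patients below eGFR 50 fall in stage 1-2. In simulated trials, the log-rank had about the same power for CKD 4 or 5 with stratification as without it (0.27 vs 0.29; 0.25 vs 0.26; 0.39 vs 0.37).

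**5. Power for time to CKD 4 or 5.** The table compares the planned stratified log-rank with a test adjusted for log baseline eGFR whose p-value comes from re-randomising treatment within strata. Inputs are assumed: about 100 patients, slopes in mL/min/year and, for the first two rows, log-uniform baseline eGFR (ranges from 30-70 to 32-120), slope SD 6, reading CV 6-8%, 18% drop-out, and events confirmed at the next visit. Each row is a separate set of 300 to 1,200 trials per scenario.

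| Slopes, placebo vs drug | Planned | Adjusted | Gain (points) |
|---|---|---|---|
| −10 vs −2 or −7 vs 0 | 0.36, 0.47, 0.62 | 0.44, 0.65, 0.82 | 8, 18, 20 |
| −10 vs −2 or −7 vs 0 | 0.59, 0.45, 0.44, 0.36 | 0.80, 0.60, 0.59, 0.43 | 21, 15, 15, 7 |
| −10 vs −2 | 0.69, 0.43 | 0.83, 0.65 | 14, 22 |
| −8 vs −4 | 0.21, 0.15 | 0.33, 0.20 | 12, 5 |
| −6 vs −3 | 0.15, 0.09 | 0.17, 0.11 | 2, 2 |
| −6 vs −3 or −5 vs −2 | 0.06-0.15 | 0.09-0.20 | about 1-9 |

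The first row had about 8, 16 and 24 events. A still steeper pair, −15 vs −5, gave gains of 18 and 25 points; it is an extreme and is not counted in the range. Under a proportional-hazards model, with a stratified Cox model as the adjusted test, the gain was nil (0.53 vs 0.52) when the hazard rose by e^0.5 per 10 mL/min lower eGFR. At e^1.0 it was 3 to 5 points (0.33 vs 0.36; 0.42 vs 0.47).

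**6. Type I error.** The re-randomised adjusted test rejected 4-6% under no effect. Large-sample adjusted tests rejected more: 6-8% for a Cox score test, and 7.5% for a likelihood-ratio test (Monte Carlo SE about 1.1 points), against 6.2% for the log-rank in the same runs.

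**7. The other endpoints.** For the 40% fall, the re-randomised test gained about 0-8 points. A large-sample Wald test lost 11-17 points in three of four scenarios. For creatinine doubling and eGFR ≤15, about one event or fewer per trial is expected at −10 vs −2 with baseline 30-70, and power was 0.03-0.04 either way.

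**8. Events.** Schoenfeld, 1:1, two-sided 0.05, 80% power: events = 4·(1.96 + 0.8416)²/(ln HR)². At HR 0.4, 31.4/0.840 gives 38; at HR 0.5, 31.4/0.480 gives 66. With 20 events, power is 0.54 and 0.34.

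**The case against.** The planned test is valid, pre-specified, and consistent with the stratified randomisation and the stratified primary test. No stated figure is contradicted, because the plan claims power only for the primary endpoint. The larger gains assume that the drug removes 80% (−10 vs −2) to 100% (−7 vs 0) of the decline; where it removes 50-60%, the gain shrinks and can be negligible. Adjustment also adds no events. All of this stands, and it limits the point to lost efficiency on a secondary endpoint.

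A reader might go further and infer that baseline eGFR is left out altogether. The documents do not support that: eGFR below 50 is one of the two scored components, stage 3 lies wholly below 50, and under the assumptions in step 4 mean eGFR is about 63-69 in stage 1-2 against 41 in stage 3. The information is diluted, not absent. Nor do the documents say that baseline eGFR is the strongest predictor; its importance is a fair inference for thresholds fixed in absolute eGFR.

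A reader might also extend the loss to all four endpoints. Two of them are measured against the patient's own baseline, so the 6% versus 67% argument does not apply to them. For eGFR ≤15 or dialysis, too few events are likely for a covariate to help.

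**Conclusion.** The point holds for time to CKD 4 or 5, as an efficiency weakness and not an error. It assumes that the unnamed strata are the randomisation factors and that the test is two-sided. The loss is roughly 7-22 points of power if the drug removes most of the decline (−10 vs −2 or −7 vs 0 mL/min/year), about 1-12 points for smaller effects (−8 vs −4, −6 vs −3 or −5 vs −2), and 0-5 points under proportional hazards. Gains of 1 or 2 points are hardly distinguishable from none, since each power figure near 0.15 has a Monte Carlo standard error of about √(0.15·0.85/400) = 0.018. No slope, eGFR distribution or event count in the documents allows a choice among these ranges. In most scenarios the endpoint stays underpowered even after adjustment, because events are few.

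**What to change.** In Section 8.3.2 and the synopsis, before unblinding:

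- Name the strata and state the sidedness of the time-to-event tests.
- For time to CKD 4 or 5, pre-specify a covariate-adjusted log-rank: fit a Cox model with log baseline eGFR and without treatment, compare its residuals between arms, and take the p-value from re-randomising treatment within the randomisation strata. A large-sample adjusted p-value should not be relied on, given the 6-8% null rejection.
- Report the hazard ratio adjusted for baseline eGFR.
- Keep the Kaplan-Meier curves and the unadjusted stratified log-rank as supportive.
- The same adjustment may be used for the 40% eGFR fall, where about 0-8 points may be gained. No gain is claimed for creatinine doubling or for eGFR ≤15 or dialysis.

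The cost is a few lines of text and modest programming, with no new data. There are two downsides: the hazard ratio becomes conditional on baseline eGFR, and a re-randomisation routine has to be written and validated.
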